#### **8.2.3.2. Specimen Shipment**

Specific instructions on specimen shipping will be provided in the Manual of Procedures for this study.

## **9. DMID SAFETY REPORTING AND SAFETY MONITORING**

Regulatory requirements including the Food and Drug Administration (FDA) regulations, International Conference on Harmonisation (ICH) Guidelines for Good Clinical Practice (GCP), and European Union (EU) Clinical Trials Directive set forth safety monitoring and reporting responsibilities of sponsors and investigators to ensure the safety and protection of human subjects participating in clinical trials.

### **9.1. Responsibilities**

Investigators participating in this clinical trial are responsible for and will:

- Evaluate subject safety including assessment of adverse events (AEs) for seriousness, severity, and causality;
- Notify the Central Unit (the Central Unit notifies the sponsor, DMID), of protocol-defined serious adverse events (SAEs) within 24 hours; (details provided in the MOP)
- Provide detailed written reports, including necessary documentation requested by the sponsor or institutional review board (IRB)/independent ethics committee (IEC), promptly following immediate initial reports; and
- Inform the IRB/IEC of AEs as required by applicable regulatory requirements.

### **9.2. Adverse Event (AE)**

#### **9.2.1. Definition of an Adverse Event**

Any unfavorable and unintended sign (including an abnormal laboratory finding), symptom, or disease temporally associated with the use of medicinal (investigational) product whether or not considered drug related. The occurrence of an AE may come to the attention of study personnel during study visits and interviews of a study recipient presenting for medical care, or upon review by a study monitor.

#### **9.2.2. Documentation of Reportable Adverse Events**

Information to be collected on reportable AEs includes event description, time of onset, clinician's assessment of severity, relationship to study product (assessed only by those with the training and authority to make a diagnosis, which would include MD or DO), and time of

resolution/stabilization of the event. All AEs occurring from Study Day 1 through four weeks following the last dose of study drug must be documented appropriately regardless of relationship. All AEs will be followed to adequate resolution. SAE reporting is described in section 9.5.

Any medical condition that is present at the time that the patient is randomized should be considered as a baseline condition and not reported as an AE. However, if the event meets the criteria in Section 9.2.1 and the grade of the event worsens at any time during the study, it should be recorded as an AE.

### **9.3. Investigator's Assessment of Adverse Event**

The determination of seriousness, severity, and causality will be made by an on-site investigator who is qualified (licensed) to diagnose AE information, provide a medical evaluation of AEs, and classify AEs based upon medical judgment. This includes MD or DO. Events will be identified by assessing the subject at each visit. If a subject is hospitalized, the medical record should be reviewed to identify AEs. The PI is responsible for identifying and reporting AEs according to protocol guidelines.

#### **9.3.1. Assessment of Seriousness**

Event seriousness will be determined according to the protocol definition of an SAE (see Section 9.5).

#### **9.3.2. Assessment of Severity**

All reportable AEs will be graded according to the DIADS Toxicity Table (Appendix B).

#### **9.3.3. Assessment of Relationship to Study Product**

**Relationship to Study Products:** The clinician's assessment of an AE's relationship to valganciclovir study drug is part of the documentation process, but it is not a factor in determining what is or is not reported in the study. If there is any doubt as to whether a clinical observation is an AE, the event should be reported. All AEs must have their relationship to study product assessed using the terms: related or not related. In a clinical trial, the study product must always be suspect.

The investigator must provide an assessment of relationship of AEs to the study product based on:

- Temporal relationship of the event to the administration of study product;

- Whether an alternative etiology has been identified;
- Biological plausibility; and
- Existing therapy, and/or concomitant medications.

To help assess, the following guidelines are used:

- Related– There is a reasonable possibility that the study product caused the adverse event. Reasonable possibility means that there is evidence to suggest a causal relationship between the study product and the adverse event.
- Not Related– There is **not** a reasonable possibility that the administration of the study product caused the event.

## **9.4. Study Related Adverse Events**

In earlier investigations of ganciclovir and valganciclovir in infants, the side effect that was seen commonly was neutropenia. Therefore, neutropenia occurring during the course of the treatment period of the study will be assumed to be associated with study medication.

- The study drug related and expected adverse events as documented from prior studies consist of:
  - anemia
  - neutropenia
  - diarrhea, and
  - elevated alanine aminotransferase (ALT).

## **9.5. Serious Adverse Event (SAE)**

### **9.5.1. Definition of a Serious Adverse Event**

An adverse event or suspected adverse reaction is considered “serious” if, in the view of either the investigator or sponsor, it results in any of the following outcomes:

- Death,
- a life-threatening adverse event\*,

- inpatient hospitalization or prolongation of existing hospitalization,
- a persistent or significant incapacity or substantial disruption of the ability to conduct normal life functions, or
- a congenital anomaly/birth defect.
- Important medical events that may not result in death, be life-threatening, or require hospitalizations may be considered serious when, based upon appropriate medical judgment they may jeopardize the patient or subject and may require medical or surgical intervention to prevent one of the outcomes listed in this definition. Examples of such medical events include allergic bronchospasm requiring intensive treatment in an emergency room or at home, blood dyscrasias or convulsions that do not result in inpatient hospitalization, or the development of drug dependency or drug abuse.

\* Life-threatening adverse event. An adverse event is considered “life-threatening” if, in the view of either the investigator or sponsor, its occurrence places the patient or subject at immediate risk of death. It does not include an adverse event that, had it occurred in a more severe form, might have caused death.

Events related to cochlear implantation will be recorded on the CRF, but will not be considered an AE or SAE unless meeting one or more of the above outcomes:

All SAEs will be:

- recorded on the appropriate SAE eCRF
- followed through resolution or stabilization by a study clinician
- reviewed and evaluated by a study clinician

### **9.5.2. Reporting Interval**

Document all AEs and SAEs from Study Day 1 through four weeks following the last dose of study drug.

All AEs and SAEs will be followed until resolution, even if this extends beyond the study-reporting period. Resolution of an AE is defined as the return to pretreatment status or stabilization of the condition with the expectation that it will remain chronic.

At any time after completion of the study, if the investigator becomes aware of an SAE that is suspected to be related to study product, the investigator will report the event.

### **9.5.3. Notification of the Sponsor of Serious Adverse Events**

When a site identifies any SAE that meets the protocol-defined serious criterion, a call will first be made to the Clinical Studies Administrator at the Central Unit. Within 24 hours of identification, the SAE will be entered into the eCRF and the original signed SAE document will be faxed to the Central Unit. If a signature from the PI is not obtained within 24 hours, it will be faxed without the signature.

[contact] to the attention of Central Unit Safety Coordinator.

The Central Unit will report all serious adverse events to DMID pharmacovigilance contractor, at the following email address: SAE Email address - [[contact]](mailto:[contact]).

Should it be necessary for the Central Unit to contact the DMID Pharmacovigilance Group the following is contact information:

DMID Pharmacovigilance Group  
Clinical Research Operations and Management Support (CROMS)  
[name]  
[name]  
SAE Hot Line: [name] (US) or [name] (outside US)  
SAE FAX [contact] (US) or [name] (outside US)

Other supporting documentation of the event may be requested by the DMID pharmacovigilance contractor and should be provided as soon as possible. The DMID pharmacovigilance contractor will notify the DMID medical monitor and clinical protocol manager. The DMID medical monitor will review and assess the SAE for regulatory reporting and potential impact on study subject safety and protocol conduct. At any time after completion of the study, if the investigator becomes aware of an SAE that is suspected to be related to study product, the investigator will report the event to the DMID Pharmacovigilance Group.

### **9.5.4. Regulatory Reporting for Studies Conducted Under DMID-Sponsored IND**

Following notification from the Central Unit DMID, the IND sponsor, will report to FDA any suspected adverse reaction that is both serious and unexpected. DMID will report an adverse event as a suspected adverse reaction only if there is evidence to suggest a causal relationship between the drug and the adverse event. DMID will notify FDA and all participating investigators (i.e., all investigators to whom the sponsor is providing drug under its INDs or under any investigator's IND) and the Central Unit in an IND safety report of potential serious risks from clinical trials or any other source, as soon as possible, but in no case later than 15 calendar days after the sponsor determines that the information qualifies for reporting as specified in 21 CFR Part 312.32. DMID will also notify FDA of any unexpected fatal or life-

threatening suspected adverse reaction as soon as possible but in no case later than 7 calendar days after the sponsor's initial receipt of the information. Relevant follow-up information to an IND safety report will be submitted as soon as the information is available. Upon request from FDA, DMID will submit to FDA any additional data or information that the agency deems necessary, as soon as possible, but in no case later than 15 calendar days after receiving the request.

All serious events designated as "not related" to study product(s), will be reported by DMID to the FDA at least annually in a summary format.

The Site Investigator is responsible for informing the Ethics Committee and/or IRB of the SAE as per local requirements. For non-US sites, the site investigator is responsible for also informing their Regulatory Authority as required by their local regulations.

## **9.6. Halting Rules**

### **9.6.1. Discontinuation of Study participation for individual subject**

Subjects with neutropenia, thrombocytopenia, renal impairment, or hepatotoxicity will be discontinued from study treatment if the criteria outlined in Section 6.3 are met. Since the primary endpoint requires comparison of baseline and 6 month audiology assessments, dropouts and subjects with audiology assessments that are inadequate for study comparison will be replaced in order to reach the target of sample size.

### **9.6.2. Discontinuation of Study Enrollment Pending Sponsor Review**

In prior CASG studies of ganciclovir and valganciclovir that have enrolled 233 subjects, the only laboratory toxicity statistically associated with antiviral treatment has been neutropenia. Halting rules for this study therefore have been constructed to interrupt study enrollment if an excessive number of subjects are experiencing neutropenia. In the CASG 102 study, 63% of subjects receiving parenteral ganciclovir developed Grade 3 or Grade 4 neutropenia. In the CASG 109 study, 38% of subjects receiving oral valganciclovir developed Grade 3 or Grade 4 neutropenia. Whether this lower rate of neutropenia relates to the mode of drug delivery is not known at this time. Assuming that 75% of subjects receiving ganciclovir developed Grade 3 or 4 neutropenia and given that randomization is expected to be balanced between those in study drug and those in placebo, the stopping rule will be based on assuming that the overall event rate for all study participants (i.e., placebo and active subjects combined) is 37.5%. Therefore, study enrollment will be stopped and an ad hoc review will be performed if a significantly higher proportion (37.5%) of subjects in this study experience Grade 3 or Grade 4 neutropenia, as detailed in the following table:

X of the first Y subjects enrolled have Grade 3 or Grade 4 neutropenia, according to the table below. The stopping rules are based on the upper tail probabilities of the cumulative binomial with probability of an event set at 0.375. The cut-off numbers were determined by obtaining the largest value such that the tail probability is less than but closest to 0.05.

Number enrolled (Y)	Stop/Investigate when number with events equals this number (X)	Probability of observing X or more events assuming p=0.375	Number enrolled (Y)	Stop/Investigate when number with events equals this number (X)	Probability of observing X or more events assuming p=0.375
4	4	0.020	30	17	0.025
5	5	0.007	31	17	0.037
6	5	0.031	32	18	0.024
7	6	0.013	33	18	0.034
8	6	0.036	34	18	0.048
9	7	0.017	35	19	0.032
10	7	0.038	36	19	0.044
11	8	0.019	37	20	0.030
12	8	0.039	38	20	0.041
13	9	0.021	39	21	0.028
14	9	0.039	40	21	0.038
15	10	0.021	41	22	0.026
16	10	0.037	42	22	0.035
17	11	0.021	43	22	0.047
18	11	0.036	44	23	0.032
19	12	0.021	45	23	0.043
20	12	0.034	46	24	0.030
21	13	0.020	47	24	0.040
22	13	0.033	48	25	0.028
23	13	0.050	49	25	0.037
24	14	0.031	50	25	0.048
25	14	0.046	51	26	0.034
26	15	0.029	52	26	0.044
27	15	0.043	53	27	0.032
28	16	0.027	54	27	0.041
29	16	0.040			

Additionally, DMID and the Central Unit may interrupt study dosing and/or study entry at any time if medically indicated. To minimize risk, the medical monitor and the DSMB will review cumulative safety data. If enrollment is halted based upon the table above or the review of the safety data, upon completion of the review and receipt of advice of the DSMB, DMID and the Central Unit Administration will determine if study entry or study dosing may continue according to the protocol.

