### **2.1.1. Retrospective diagnosis of congenital CMV**

Clinical investigators are now diagnosing congenital CMV infection retrospectively when older children present with hearing loss by means of PCR testing on stored dried blood spots (DBS; Guthrie cards) which had been obtained during the neonatal period. While the sensitivity of DBS PCR is variable (34-100%), the specificity is high (99-100%) such that a positive result confirms congenital CMV infection while a negative result does not rule out a congenital CMV infection. Walter et al. conducted a study using quantitative PCR to extend these results and determine if there was a threshold value of CMV genomes in a DBS above which hearing loss occurred more frequently. Briefly, DBS were created from fresh blood known to be CMV PCR positive at various levels of viral load and tested on multiple occasions. Guthrie cards were also created from fresh blood known to be CMV PCR negative and stored at room temperature adjacent to CMV-positive cards to facilitate any possible cross-contamination. Over a 12 month period, 43 negative DBS gave negative results (specificity 100%) and 39 positive DBS gave positive results (sensitivity 100%). Compared to the viral load found in each fresh whole blood, the viral load from the DBS was initially approximately 2 logs lower but remained stable for at least 2 years. These results show that the sensitivity of DBS is slightly lower than that of whole blood (cut-off 1000 genomes/ml vs 200 genomes/ml) but that DBS retrieved from children of the age required for this study should give reliable results. Additionally, the stored DBS of 39 children (aged 2 months-13 yrs at time of testing) with proven congenital CMV infection and sensorineural hearing loss were retrieved, together with those from 35 children (aged 7 months to 15 years) with unexplained SNHL. These samples were tested under code by quantitative PCR. The sensitivity was 75% (28/39 known cases of congenital infection) while 23% (8/35) of

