cases of unexplained SNHL were PCR positive (similar to results of 20% and 25% previously reported for qualitative PCR). One case of a false-positive reaction was seen (child and mother both CMV seronegative). Importantly, a defined threshold effect was seen when severity of hearing loss was plotted against CMV viral load in DBS. However, the shape of this curve was so steep that, for practical purposes, the detection of any level of viremia could be considered a risk factor for future hearing loss, as previously reported by the NIAID Collaborative Antiviral Study Group (CASG). We conclude from all these results that ongoing CMV replication may be a risk factor for progressive hearing loss and that control of viral replication may be considered a potential pharmacodynamic measure of successful antiviral therapy.

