## **4. STUDY DESIGN**

This is a Phase II international, multi-center, double-blind, placebo-controlled evaluation of 6 weeks of valganciclovir treatment for children (up to 4 years of age) with virologically-confirmed congenital CMV infection and hearing loss. Patients who are between 1 month and 4 years of age and who have SNHL are eligible for enrollment on the study. **Enrollment on the study occurs when eligibility is confirmed and the informed consent is signed.** Following the signing of informed consent, the subject's Guthrie card will be retrieved and tested for CMV DNA by PCR unless there is a virologically confirmed diagnosis of congenital CMV infection made within the first 30 days of life. **Randomization on the study occurs when the diagnosis of congenital CMV infection is confirmed,** and the subject then is assigned to either receive 6 weeks of oral valganciclovir or 6 weeks of placebo. Study subjects will be stratified according to age at randomization (1 through 11 months, 12 through 23 months, 24 through 35 months, and  $\geq 36$  months) and CMV involvement (symptomatic and asymptomatic at birth) as a marker of disease severity. The sample size of randomized, evaluable subjects is 54. Dropouts and subjects with audiology assessments that are inadequate for study comparison will be replaced (up to 20%, or  $n=10$ ). Baseline study assessments (see Section 7.2) will be performed following randomization. Subjects will be followed for 6 months post randomization. During the six week treatment period, study subjects will be followed every 2 weeks. Subjects will also be seen at approximately one month following the final dose (Study Day 70), and again at Study Months 4 and 6.

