#### **5.4.3. Reasons for Withdrawal Before Randomization**

The criteria for discontinuation of study participation following enrollment and before randomization include:

- Failure to confirm congenital CMV infection
- Study subject (parent/legal guardian) wishes to withdraw
- Trial termination (by UAB Central Unit, FDA, DMID, NIAID, NIH, UCL, or agreement of all investigators) issued per safety or efficacy criteria
- Any other reason which, in the opinion of the investigator, precludes the study subject's participation in the study. The principal investigator must call the Protocol Chair (or designee) prior to discontinuing a study subject for this reason.

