#### **5.4.6. Handling of Withdrawals**

Study subjects may withdraw voluntarily from participation in the study at any time. Up to 20% (n=10) over-enrollment is allowed to replace subjects who drop-out or who have inadequate audiology assessments. Study subjects also may withdraw voluntarily from receiving the study intervention for any reason. If a study subject withdraws or is discontinued from the study at any time prior to completion of the study, the reason for this decision will be recorded on the electronic case report form (eCRF). SAEs and AEs will be followed according to guidelines in Section 9. The study subject should be encouraged to complete follow-up visits as part of the intent to treat group.

Should a study subject's therapy be discontinued prematurely, all clinical and laboratory evaluations scheduled during the next study visit will be completed on the day the study subject is discontinued. All randomized study subjects will continue to be followed as long as possible and included in the final analysis.

Since the primary endpoint requires comparison of baseline and 6 month audiology assessments, dropouts and subjects with audiology assessments that are inadequate for study comparison (Section 11.4.1) will be replaced. Characteristics of the dropouts and those with missing outcomes will be compared to determine if there is a difference between the two treatment groups. If differences are observed, this will be included in the primary outcome reporting as a limitation.

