### **7.1. Enrollment (Window: Day -90 to Day -1)**

Following confirmation that the patient is eligible for study enrollment and obtaining informed consent, if infection with CMV has not been documented within the first 30 days of life then the Guthrie card will be retrieved and analyzed by PCR for CMV DNA; PCR will be performed in the U.K. as part of routine clinical investigation protocols, while in the U.S. it will be performed at the UAB Central Laboratory. If the result is positive or if there is other virologic confirmation of congenital CMV infection, congenital CMV is confirmed. These subjects are eligible for randomization, following which the baseline assessments (see Section 7.2) will be obtained.

Subjects who have signed the informed consent document and therefore are enrolled on the study but who then do not qualify for randomization in the trial (for example, because the Guthrie card PCR was negative) will not be counted toward the final sample size for the study. Consented study participants may receive nominal compensation to offset the cost of travel, parking, meals, etc., for study visits in accordance with local site policies and local IRB approval.

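### The neutropenia halting table counts children enrolled (consented), but its 37.5% rate fits only randomised, treated children, and its rows stop at 54 although 64 may be randomised

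*Protocol*

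**What the plan says.** The trigger in Protocol 9.6.2, repeated in SAP 4.1, is that "X of the first Y subjects enrolled have Grade 3 or Grade 4 neutropenia, according to the table below". The table's first column, there and in SAP 6.5.2, is headed as the number enrolled.

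Enrolled is a defined term. Protocol 4 states: "Enrollment on the study occurs when eligibility is confirmed and the informed consent is signed". Protocol 5.1 repeats this, and testing of the Guthrie card follows consent. Protocol 7.1 speaks of "Subjects who have signed the informed consent document and therefore are enrolled on the study but who then do not qualify for randomization" and leaves those children out of the final sample size. Protocol 5.4.3 gives "Failure to confirm congenital CMV infection" as a reason for withdrawal after enrolment and before randomisation.

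The rate has a different basis. Protocol 9.6.2 assumes 75% Grade 3 or 4 neutropenia on active drug and balanced randomisation, and then says "the stopping rule will be based on assuming that the overall event rate for all study participants (i.e., placebo and active subjects combined) is 37.5" per cent.

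The last row is Y = 54, X = 27, with tail probability 0.041. Protocol 5.4.6 adds: "Up to 20% (n=10) over-enrollment is allowed to replace subjects who drop-out or who have inadequate audiology assessments".

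**The concern.** The binomial calculation treats all Y children as at risk at a pooled 37.5%. A consented child whose congenital infection is not confirmed is never dosed. Study haematology begins at the baseline visit after randomisation (Protocol 7.2; SAP 4.5). Such a child therefore adds one to Y and cannot add to X. Every cut-off is then too high for the number really at risk, and the error has only one direction.

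The missing rows are a separate matter. Even if Y means randomised children, numbers 55 to 64 have no cut-off. If Y means consented children, the table runs out before 54 children have been dosed as soon as one enrolled child is not dosed.

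This table is the only numerical trial-level trigger for the one laboratory toxicity that Protocol 9.6.2 describes as statistically associated with treatment. Two people applying the same text could count Y differently.

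**Working it through.** **1. Reproduce the table.** Rule: X is the smallest count with P(Bin(Y, 0.375) ≥ X) < 0.05. All 51 printed cut-offs (Y = 4 to 54) match, and all tail probabilities match to three decimals. For example, Y = 54, X = 27 gives 0.041. The arithmetic is sound.

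**2. Where 0.375 comes from.** 0.5 × 75% + 0.5 × 0% = 37.5%. A placebo rate of 0% is implied. The figure describes a treated cohort with the arms pooled, not the active arm alone, for which the assumed rate is 75%.

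**3. The last row under the literal reading.** Let f be the dosed share of enrolled children. It is not in the documents; 90% and 75% are assumed.
- f = 0.90: 0.90 × 54 ≈ 49 dosed. X = 27 is 27/49 = 55% of those at risk; the table's own row for 49 needs 25 (51%). The true tail at 0.375 is P(Bin(49, 0.375) ≥ 27) = 0.009, not 0.041.
- f = 0.75: 0.75 × 54 ≈ 40 dosed. X = 27 is 27/40 = 68%; the row for 40 needs 21 (53%).

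**4. Chance of ever halting by Y = 54.** Exact recursion over the rows, with per-child event probability f × (active rate + placebo rate)/2. It assumes simple 1:1 randomisation and each outcome known when the child is counted.

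| True rates, active/placebo (pooled) | f = 1 | f = 0.90 | f = 0.75 |
|---|---|---|---|
| Table's own rate (37.5%) | 16% | 8% | 3% |
| 75%/21% (48%) | 62% | 38% | 12% |
| 63%/21% (42%) | 33% | 17% | 5% |
| 38%/21% (29.5%) | 3.4% | 1.8% | 0.7% |

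The active rates are the assumed 75% and the 63% and 38% from earlier studies, all in Protocol 9.6.2. The 21% is the untreated neonatal rate in Protocol 2.1.2.1, borrowed here as a placebo rate.

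**5. The missing rows.** The maximum randomised is 54 + 10 = 64. The rule in step 1 gives:

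| Y | 55 | 56 | 57 | 58 | 59 | 60 | 61 | 62 | 63 | 64 |
|---|---|---|---|---|---|---|---|---|---|---|
| X | 28 | 28 | 28 | 29 | 29 | 30 | 30 | 31 | 31 | 31 |
| Tail | 0.029 | 0.038 | 0.048 | 0.035 | 0.045 | 0.032 | 0.041 | 0.030 | 0.038 | 0.048 |

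With every counted child dosed, running the table to 64 raises the chance of ever halting from 16.2% to 17.4% at 37.5%, from 62% to 68% at 75%/21%, and from 3.4% to 3.5% at 38%/21%.

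**The case against.** The strongest reply is that nobody would apply the literal reading. The section names placebo and active subjects combined and refers to balanced randomisation. The rows end at 54, which is the randomised target. SAP 5 calls 54 the planned enrolment, and Protocol 5.4.6 calls the replacements over-enrolment. This stands as evidence of intent. It does not remove the clash with a term that the protocol defines and then applies expressly to children who are not randomised.

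It is also fair that the sizes depend on assumptions. A reader might take the fall from 62% to 12% as an estimate for this trial. The documents do not support that: the dosed share is not given, and 75%/21% is an illustration. At 38%/21%, which uses the only rate quoted for oral valganciclovir, the loss at 90% dosed is from 3.4% to 1.8%. Protocol 2.1.1 reports that 23% (8/35) of children with unexplained hearing loss were PCR positive, so unconfirmed infection is foreseeable. But those children were aged 7 months to 15 years, the share entering this trial through the Guthrie card is unknown, and Protocol 7.1 accepts other virological confirmation.

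The ten missing rows matter little numerically, since few children remain to be entered by then. The gap nevertheless exists under either reading of Y.

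Finally, a reader might infer that the trial is left unprotected. It is not. Individual neutrophil rules (Protocol 6.3.1), interruption at the discretion of the sponsor and Central Unit (Protocol 9.6.2), and DSMB review remain. SAP 4.4 provides closed reports with unblinded information, although DSMB access is left to the charter.

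**Conclusion.** The point holds as a contradiction in a decision rule. The counting unit, as defined, includes children who cannot have an event; the reference rate excludes them; and the rows stop ten short of the permitted number randomised. It would be wrong to conclude that the table is miscalculated, since every printed row is correct, or that the team counts consented children, which nothing in the documents shows.

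If the wording is followed, the chance of halting at the table's own rate roughly halves at 90% dosed (16% to 8%) and falls to 3% at 75%. These figures rest on assumed dosed fractions and, in the other scenarios, on a borrowed placebo rate. If the team already counts treated children, the practical effect is confined to the ten missing rows. The matter should be fixed because the direction is always towards a weaker trigger and the remedy is small.

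**What to change.** Reconcile Protocol 9.6.2 with Protocol 4, 5.1 and 7.1, and make the same change in SAP 4.1 and 6.5.2:

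- Give Y one stated denominator that matches the 0.375 rate: randomised children who received at least one dose of valganciclovir or placebo, arms pooled, in order of first dose. State when a child is counted, because the first on-treatment neutrophil count is scheduled for Day 14.
- Reconcile the safety populations too. SAP 6.2 uses all enrolled participants, SAP 9 uses those with at least one dose, and Protocol 11.2 uses dosed children with complete hearing data. The SAP therefore cannot be said to have settled on dosed children already.
- Make the table cover the permitted maximum of 64. The protocol's own formula gives the rows in step 5 of the working.

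The acceptable neutropenia rate and any decision to halt stay with the sponsor and DSMB.

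The cost is a protocol and SAP amendment, with IRB approval before use (Protocol 14.2) across 17 sites. No new data or unmasking is needed. Some further ad hoc reviews are possible: against the literal reading at 90% dosed, the chance of a halt returns from 8% to 16% at the table's own rate. If treated children are already counted, only the wording and the ten rows change.
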